#### **11.6.1. Secondary Efficacy Analysis**

Secondary endpoints will be analyzed for treatment group differences. Multiple sensitivity analyses will be performed on the primary efficacy endpoints.

For categorical endpoints (e.g., proportions) a logistic regression model testing between treatment differences with terms for diabetes status and use of Vitamin E and/or pioglitazone and baseline covariate NAS included in the model. Odds ratio and the 95% confidence intervals will be reported. If convergence is encountered the Fisher's exact test will be used to test treatment group differences.

For continuous endpoints (e.g., change from baseline) an analysis of covariance (ANCOVA) model testing treatment differences with terms for baseline diabetes status and use of Vitamin E and/or pioglitazone, baseline covariate NAS, and baseline parameter of interest included in the model. A type III sum-of-squares for the least-squares means and 95% confidence intervals will be reported.

When continuous endpoints that are repeated over visits a restricted maximum likelihood-based mixed model repeated measures (MMRM) technique may be performed. The model will include treatment, baseline covariate NAS, baseline parameter, visit, treatment-by-visit interaction as fixed effects. An unstructured variance-covariance structure will be considered to model the within-patient error. If the unstructured covariance matrix results in a lack of convergence, the heterogeneous Toeplitz covariance structure should be used. The Kenward-Roger method will be used to estimate the denominator degrees of freedom. A type III sum-of-squares for the least-squares means and 95% confidence intervals will be reported.

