### **8.6.1 Analysis methods**

#### **Logistic Regression Model for proportion of responders**

Endpoints looking at a proportion of responders will be analyzed by logistic regression. The SAS procedure PROC GENMOD will be used. The preferred model will include the fixed categorical effects of treatment group, diabetes status and use of Vitamin E and/or pioglitazone. Baseline NAS score will be included as covariate. The model will be used to derive odds ratio, confidence interval and p value. A sample of SAS code for logistic regression is provided in [Appendix A](#).

Fisher exact test will be used to test the treatment difference in case the model does not converge. A sample of SAS code for Fisher exact test is provided in [Appendix A](#).

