### 8.6.2 Analysis of primary efficacy endpoint(s)

The primary efficacy analysis is a set of two primary endpoints. The primary endpoints comprise of proportion of subjects who achieve:

- $\geq 1$  stage improvement in liver fibrosis without worsening of steatohepatitis
- Resolution of steatohepatitis without worsening of liver fibrosis

as determined by liver biopsy at week 72. Derivation for steatohepatitis and fibrosis conditions (like improvement, worsening and resolution) are provided in [Table 2](#).

A responder will be defined for each primary endpoint separately. Any subject achieving the primary endpoint will be a responder for that primary endpoint. Subjects will not be categorized as responder or non-responder in case of missing response (score).

The objective related to the primary endpoint is to evaluate the effect of EDP-305 compared to placebo with respect to proportion of responders defined as above.

The hypothesis to test EDP-305 2 mg and placebo is formulated as:

- $H_{01}: OR = 1$  v/s  $H_{11}: OR \neq 1$

Where OR is the odds ratio at week 72 for EDP-305 2mg and placebo treatment groups respectively.

The hypothesis to test EDP-305 1.5 mg and placebo is formulated as:

- $H_{02}: OR = 1$  v/s  $H_{12}: OR \neq 1$

Where OR is the odds ratio at week 72 for EDP-305 1.5mg and placebo treatment groups respectively.

The proportion of responders for each endpoint will be compared using a logistic regression model with treatment group, diabetes status and use of Vitamin E and/or pioglitazone as fixed effects and baseline NAS score as covariate. Treatment groups will be compared for each endpoint at a 0.025 significance level. The odds ratio, 97.5% confidence interval and the p-value will be presented. In the event that the logistic regression model is unable to converge, a Cochran-Mantel-Haenszel test will be performed using the stratification factors of diabetes status and Vitamin E/pioglitazone use status. The frequency counts for responders and non-responders will also be presented in the table. The primary efficacy analyses will be performed using the ITT population. As an additional analysis, the primary endpoint will also be analyzed using PP population. Multiplicity control for this testing is noted in [Section 8.6.1.1](#).

A by-subject listing will be provided for the primary efficacy endpoints.

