#### 8.6.3.1 Categorical Endpoints (Responder at Week 72)

Secondary endpoints with categorical values are defined as below:

Proportion of subjects with

- improvement of fibrosis by at least 1 stage and/or resolution of NASH without worsening of either as determined by liver biopsy at week 72
- no worsening of fibrosis combined with no worsening of NASH as determined by liver biopsy at week 72
- resolution of fibrosis as determined by liver biopsy at week 72
- improvement in each histologic feature of NASH, by at least 1 point as determined by liver biopsy at week 72
- improvement of fibrosis by  $\geq 2$  stages by liver biopsy at week 72
- improvement in NAS by at least 2 points with no worsening of fibrosis as determined by liver biopsy at week 72
- improvement of fibrosis and resolution of NASH as a composite endpoint as defined by both endpoints being met in the same subject
- resolution of NASH and no worsening of liver fibrosis
- histological progression to cirrhosis as determined by liver biopsy at week 72

Any subject who satisfies the criteria for the secondary endpoint will be a responder for that endpoint.

The proportion of responders for each endpoint will be compared using a logistic regression model with treatment group, diabetes status and use of Vitamin E and/or pioglitazone as fixed effects and baseline NAS score as covariate at week 72. Treatment groups will be compared for each endpoint at a 0.05 significance level. Odds ratio, 95% confidence interval and p value will be reported in the table.

A Cochran-Mantel-Haenszel test stratifying by diabetes status and Vitamin E/pioglitazone usage will be utilized to test the treatment group differences in case of lack of convergence. The frequency counts for responders and non-responders along with the p-value will be presented in the table.

A by-subject listing will be provided for observed and derived variables.

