**RUN;**

Note:

1. Use data without any imputation.
2. Resp: Responder (Yes/No)
3. diab\_st: Baseline diabetes status
4. vitE\_pio: Use of Vitamin E and/or pioglitazone
5. Baseline\_NAS: Baseline value of NAS
6. 0.xx=level of significance to be used
7. Use numeric variables for treatment group
8. Code **trt01pn** as Placebo=0, EDP 305 2 mg=1, EDP 305 1.5 mg=2

For Primary analysis: The EDP-305 2 mg will be compared to placebo using a two-sided alpha of 0.0xx (adjusted alpha/2 ) first then if the difference is statistically significant, EDP-305 1.5 mg will be compared to placebo using a two-sided alpha of 0.0xx (adjusted alpha/2).

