#### SAS code for Fisher Exact Test

```
ods output fishersexact=fishers;
```

```
PROC FREQ data=dataset;
```

```
tables trt01pn*responder /exact out=count;
```

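### SAP 8.6.1 and SAP 8.6.2/8.6.3.1 name different fallback tests for the same non-converging responder model, and neither test is specified as the pairwise comparison the hypotheses need

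*SAP*

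**What the plan says.** The general methods in SAP 8.6.1 cover every responder endpoint: "Endpoints looking at a proportion of responders will be analyzed by logistic regression". If that model fails, "Fisher exact test will be used to test the treatment difference in case the model does not converge". Appendix A supplies sample code for the Fisher test, whose table statement is "tables trt01pn*responder /exact out=count". The note under the logistic code in the same appendix codes trt01pn "as Placebo=0, EDP 305 2 mg=1, EDP 305 1.5 mg=2", which is three levels.

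The endpoint sections say something else. For the primary endpoints, SAP 8.6.2 has: "In the event that the logistic regression model is unable to converge, a Cochran-Mantel-Haenszel test will be performed", with diabetes status and Vitamin E/pioglitazone use as strata. For the secondary responder endpoints, SAP 8.6.3.1 has: "A Cochran-Mantel-Haenszel test stratifying by diabetes status and Vitamin E/pioglitazone usage will be utilized to test the treatment group differences". No CMH code is given.

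The protocol gives no fallback for the primary model. For secondary categorical endpoints, Protocol 11.6.1 says: "If convergence is encountered the Fisher's exact test will be used to test treatment group differences".

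The primary hypotheses in SAP 8.6.2 are pairwise: 2 mg against placebo, and 1.5 mg against placebo. SAP 8.6.1.1 and Protocol 11.6 test 2 mg first, two-sided at 0.025 for each primary endpoint, and go on to 1.5 mg only if 2 mg is significant.

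**The concern.** One event, failure of the logistic model to converge, leads to two different tests depending on which SAP section is read. One ignores the randomisation strata and the other uses them. They can fall on opposite sides of the significance level with the same data, so the choice should be fixed before unblinding.

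The printed Fisher code also answers a different question from the hypotheses. It asks whether response differs anywhere among three arms. The step-down asks first whether 2 mg differs from placebo. A difference carried entirely by the 1.5 mg arm can make the omnibus p-value small, and a clear 2 mg effect can be diluted when the third arm lies in between. For a primary endpoint this could wrongly permit or wrongly block the 1.5 mg test. For secondary endpoints, which are tested at 0.05 with no ordering, the omnibus p-value does not say which dose differs from placebo.

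**Working it through.** **1. The plan's own figures.** The alpha for each primary endpoint is 0.05 / 2 = 0.025, as SAP 8.6.1.1 states. Arm size is 112 (SAP 3.3.1), and 3 x 112 = 336 agrees with Protocol section 3. The sample-size section is redacted, so no planned response rates are available. All responder counts and stratum sizes below are assumptions chosen for illustration, with no missing biopsies and no interim adjustment of alpha.

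**2. The rules side by side.**

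| Place | Endpoints | Fallback | Two arms at a time? |
|---|---|---|---|
| SAP 8.6.1, Appendix A | all responder endpoints | Fisher, unstratified | no; code uses three-level trt01pn with no subsetting |
| SAP 8.6.2 | primary | CMH, two stratification factors | not stated |
| SAP 8.6.3.1 | secondary responder | CMH, same factors | not stated |
| Protocol 11.6.1 | secondary categorical | Fisher | not stated |

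The sample logistic code does produce pairwise differences, through its lsmeans pdiff option. The Fisher code has no equivalent.

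**3. Omnibus against pairwise Fisher.** With responders a, b, c in placebo, 2 mg and 1.5 mg, the three-arm exact probability of a table is

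C(112,a) x C(112,b) x C(112,c) / C(336, a+b+c),

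and the p-value sums this over all tables with the same total that are no more probable than the one observed. The pairwise version uses C(112,a) x C(112,b) / C(224, a+b).

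| Responders (placebo, 2 mg, 1.5 mg) | Three-arm p | 2 mg vs placebo p | 1.5 mg vs placebo p |
|---|---|---|---|
| 13, 13, 30 (total 56) | 0.0035 | 1.00 | 0.0062 |
| 13, 27, 24 (total 64) | 0.037 | 0.0225 | 0.071 |

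In the first row the omnibus result is below 0.025, so 1.5 mg would be tested although 2 mg and placebo are identical. In the second the omnibus result is above 0.025, so testing would stop although 2 mg vs placebo meets the criterion.

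**4. CMH against Fisher on the same two arms.** Assume 26 responders on 2 mg and 13 on placebo, in four strata of 60, 32, 12 and 8 per arm, with responders 13 vs 5, 8 vs 5, 3 vs 2 and 2 vs 1.

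- Expected 2 mg responders: 9 + 6.5 + 2.5 + 1.5 = 19.5. Observed minus expected: 26 - 19.5 = 6.5.
- Variance per stratum is n1 x n2 x m1 x m2 / (N² x (N-1)), with n the arm sizes, m1 and m2 the responders and non-responders, and N = n1 + n2. This gives 3.857 + 2.631 + 1.033 + 0.650 = 8.171.
- CMH chi-square without continuity correction: 6.5² / 8.171 = 5.17, p = 0.023.
- Pairwise Fisher on 26/112 vs 13/112: p = 0.034.

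The two named tests disagree at 0.025. With a continuity correction the CMH p-value is 0.036 and the disagreement disappears; the SAP does not say which form is meant.

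**The case against.** **The specific section should govern.** SAP 8.6.2 and 8.6.3.1 are endpoint-specific and agree with each other, so a careful analyst would probably use CMH and treat the Fisher text as a leftover. Protocol 11.1 lets the SAP change methods that are not principal features. This is a fair reading, but the SAP does not state it. Under it Fisher would apply to no endpoint listed in 8.6.2 or 8.6.3.1, yet 8.6.1 and Appendix A keep it and give code for it alone. Section 9, headed as changes from the protocol, does not record the switch from Fisher to CMH.

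**The code is only a sample.** The data set name is a placeholder, and a programmer who reads the pairwise hypotheses could subset to two arms. So a reader should not infer that the plan makes a pairwise Fisher test impossible. The supported statement is that the code as printed is not pairwise and that nothing instructs the programmer to subset.

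**The fallback would rarely run on a primary endpoint.** This largely stands. With 12, 26 and 20 responders per 100 and covariates unrelated to response (half the subjects diabetic), the logistic fit failed in about 6%, 0.3% and 0% of simulated data sets when Vitamin E/pioglitazone use was 5%, 10% and 20%. Failure was common, about 13% to 58%, only at very sparse counts such as 1, 1 and 8 per 100, and the documents do not show that a primary endpoint would be that sparse. If Fisher is run on every simulated trial at true rates of 12%, 12% and 24%, the three-arm test falls below 0.025 in 58% of trials and the 2 mg vs placebo test in 1.4%. A reader might take 58% as an error rate of this plan. It is not, because it ignores the requirement that the model first fail.

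**The sparse endpoints have no step-down.** This stands. Resolution of fibrosis, improvement by two or more stages and progression to cirrhosis are secondary. SAP 8.6.1.1 confines the multiplicity adjustment to the primary analysis, and 8.6.3.1 tests each secondary endpoint at 0.05. It would be wrong to infer that the omnibus test could open or close the 1.5 mg comparison for them.

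**The protocol sentence is a slip.** This also stands. Read literally, Protocol 11.6.1 runs Fisher when the model converges, but non-convergence is plainly meant.

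**Conclusion.** The fallback rule is contradictory, and its only printed code does not test the stated hypotheses. Both points rest on the text alone. The size of the consequence rests on assumed counts. At 112 per arm the omnibus and pairwise p-values can differ as widely as 0.0035 and 1.00, and they can err in either direction (0.037 against 0.0225). Uncorrected CMH and pairwise Fisher can also fall on opposite sides of 0.025 (0.023 against 0.034).

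For the primary endpoints this matters only if the logistic model does not converge, which looks unlikely at moderate response rates. For the sparse secondary endpoints non-convergence is more plausible, but the harm is limited to an unfixed choice of test and a p-value that names no dose.

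A reader might infer that a reported result is at risk. The documents do not support that: SAP section 9 records that the study ended before any subject had completed the Week 72 assessments, and it drops the primary, secondary responder and second interim analyses. The point corrects the plan, and would matter in practice if its text or code were reused.

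**What to change.** - Keep one fallback throughout: the stratified CMH test already named in SAP 8.6.2 and 8.6.3.1. State whether a continuity correction is used.
- State that it is run on two-arm data, 2 mg vs placebo and then 1.5 mg vs placebo. For the primary endpoints use the primary alpha (0.025, or the adjusted value if an interim look is taken) with the step-down. For secondary endpoints use 0.05 with no ordering. Naming CMH without this sentence would leave the pairwise gap open.
- In SAP 8.6.1 and Appendix A, delete the Fisher paragraph and code, or restrict them to two-arm data with a stated use. Add matching CMH code.
- Align Protocol 11.6.1 with the SAP and correct its wording so that it refers to failure to converge. If the protocol is left as it is, record the change and the reason in SAP section 9.

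Firth-penalised logistic regression would be a reasonable alternative for sparse endpoints, but the documents do not require it. The cost is a few sentences in the SAP, one in the protocol, and a few lines of code, with no change to design, sample size or data collection.

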#### **Analysis of Covariance (ANCOVA) Model for Change from baseline**

In summaries of efficacy endpoints examining change from baseline at week 12 and week 72, ANCOVA of the differences between post-baseline and baseline measurements will be performed, with treatment group, baseline diabetes status and use of Vitamin E and/or pioglitazone as fixed effect and the baseline measurement of the parameter of interest along with baseline NAS score as covariate. A sample of SAS code for ANCOVA model is provided in [Appendix A](#).

The model will provide the least-squares means (using type III sum-of-squares), standard errors, p-value and 2-sided 95% confidence interval for treatment differences.

#### **Mixed Model Repeated Measures (MMRM) analysis**

A MMRM analysis will be performed for secondary efficacy endpoints that are continuous in nature and assessed over multiple study visits. The SAS procedure PROC MIXED will be used. The preferred model will include the fixed categorical effects of treatment group, visit, treatment-by-visit interaction as well as the continuous fixed covariates of baseline measurement for the parameter of interest and baseline NAS score. An unstructured variance-covariance structure will be considered to model the within-patient error. If the unstructured covariance matrix results in a lack of convergence, the heterogeneous Toeplitz covariance structure should be used. The Kenward-Roger method will be used to estimate the denominator degrees of freedom. A sample of SAS code for MMRM is provided in [Appendix A](#).

The model will provide least-squares means (using type III sum-of-squares), standard errors, p-value and 2-sided 95% confidence interval for treatment differences for each visit.

[figure not shown]

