## **5.6. Treatment Assignment/ Randomization**

Subjects will be randomized to study treatment using an IWRS. Subjects will be randomized to the treatment groups shown below:

- Treatment Group 1 (N=112); EDP-305 1.5 mg orally for 72 weeks
- Treatment Group 2 (N=112); EDP-305 2 mg orally for 72 weeks
- Treatment Group 3 (N=112); Placebo orally for 72 weeks

In addition, subjects will be stratified based on 1) use of Vitamin E and/or pioglitazone and 2) type 2 diabetes mellitus (T2DM) status.

The randomization code will be produced by Enanta (or designee). The Enanta unblinded biostatistician or designee will review and approve the final randomization list.

During the Screening period, subjects will be identified by a unique Screening number assigned by the clinical site. Subjects who have completed Screening assessments and are eligible for participation in the study will be randomized before the first dose of study drug (Day -1 or Day 1) and assigned a unique subject number which will be used to identify the subject throughout the study.

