### 3.4 Study treatments and assessments

Subjects who meet all criteria for enrollment will be randomized to blinded treatment on Day 1 in a 1:1:1 ratio to EDP-305 2 mg, EDP-305 1.5 mg, or placebo. Assignment to treatment groups will be determined by a computer-generated random sequence using an IWRS. The IWRS will be used to assign double-blind investigational product to each subject. To achieve between-group comparability the randomization will be stratified by diabetes status and use of Vitamin E and/or pioglitazone.

A detailed description of procedures and assessments to be conducted during this study is summarized in the scheduled of study assessments in table below.

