#### **8.6.3.2.1 Change from baseline in 5D-itch scale and Visual Analog Score (VAS) through week 72**

Pruritus will be monitored in this study at day 1, 7, weeks 2, 4, 8, 12, 16, 20, 24, 28, 32, 36, 40, 44, 48, 56, 64, 72 and EOS.

Observed values, change from baseline, and percentage change from baseline for VAS scores and each dimension of 5D-itch scale and overall score will be summarized using an 8-number summary by visit and treatment group.

Change from baseline for VAS and 5D-itch scale will be analyzed using a restricted maximum likelihood-based mixed model repeated measures (MMRM) technique. The model will include treatment, visit, treatment-by-visit interaction as fixed effects along with baseline NAS score and baseline score for VAS and 5D-itch scale as covariate respectively. Variance-covariance structure to be used to model the within-patient error and results to be presented are described in [Section 8.6.1](#). The details for calculation of score is given in [Appendix B](#).

A by-subject listing will be provided for observed and derived variables for VAS and 5D-itch scale.

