## Final Analysis Statistical Analysis Plan (SAP)

of Vitamin E and/or pioglitazone as fixed effect along with baseline NAS score and baseline MRE value as covariate. Least-squares means (using type III sum-of-squares), standard errors, p-value and 2-sided 95% confidence interval for treatment differences will be presented for week 12 and week 72. Significance tests will be based on least-squares means using a two-sided  $\alpha = 0.05$ .

A by-subject listing will be provided for observed and derived variables.

### 8.6.3.2.4 Change from baseline in TG, total cholesterol (TC), HDL cholesterol, LDL cholesterol and adiponectin through week 72

The parameters, TG, TC, HDL cholesterol, LDL cholesterol and adiponectin are captured in lipid profile panel. All these parameters will be monitored in this study at day 1, weeks 2, 4, 8, 12, 16, 20, 24, 28, 32, 36, 40, 44, 48, 56, 64, 72 and EOS.

Observed values, change from baseline, and percentage change from baseline for the parameters triglyceride (TG), total cholesterol (TC), HDL cholesterol, LDL cholesterol and adiponectin will be summarized using an 8-number summary by visit and treatment group.

Change from baseline for each of the above parameters will be analyzed separately using a restricted maximum likelihood-based mixed model repeated measures (MMRM) technique. The model will include treatment, visit, treatment-by-visit interaction as fixed effects along with baseline NAS score and baseline value of the respective parameters as covariate. Variance-covariance structure to be used to model the within-patient error and results to be presented are described in [Section 8.6.1](#).

A by-subject listing will be provided for observed and derived variables.

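### The itch and lipid MMRMs omit, without a stated reason, both randomisation stratification factors that the logistic and ANCOVA models include, at a modest cost in precision

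*SAP*

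**What the plan says.** **Randomisation.** Protocol 5.6 says "subjects will be stratified based on 1) use of Vitamin E and/or pioglitazone and 2) type 2 diabetes mellitus (T2DM) status". SAP 3.4 gives the purpose: "To achieve between-group comparability the randomization will be stratified by diabetes status and use of Vitamin E and/or pioglitazone".

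**Models that carry the factors.** The logistic models for the primary and categorical secondary endpoints include both. So do the ANCOVAs for MRI-PDFF and MRE; the general ANCOVA text in SAP 8.6.1 reads "with treatment group, baseline diabetes status and use of Vitamin E and/or pioglitazone as fixed effect".

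**Models that do not.**
- General MMRM, SAP 8.6.1: "The preferred model will include the fixed categorical effects of treatment group, visit, treatment-by-visit interaction as well as the continuous fixed covariates", followed by the parameter's baseline value and baseline NAS.
- Itch, SAP 8.6.3.2.1: "The model will include treatment, visit, treatment-by-visit interaction as fixed effects along with baseline NAS score and baseline score for VAS and 5D-itch scale".
- Lipids, SAP 8.6.3.2.4: "The model will include treatment, visit, treatment-by-visit interaction as fixed effects along with baseline NAS score and baseline value of the respective parameters as covariate".
- Appendix A: the MMRM code has neither `diab_st` nor `vitE_pio`, while the ANCOVA code has both.
- Protocol 11.6.1: "The model will include treatment, baseline covariate NAS, baseline parameter, visit, treatment-by-visit interaction as fixed effects".

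The subgroup MMRM in SAP 8.9 also omits both, beside subgroup logistic and ANCOVA models that keep them. Neither document explains the difference.

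**Scope after termination.** SAP section 9 allows only summary statistics after Week 12. It cancels all subgroup analyses and the adiponectin analysis. It does not list the itch or the TG, TC, HDL and LDL models among the cancelled analyses.

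**The concern.** When allocation is balanced within strata, the strata's contribution to the outcome largely cancels out of the treatment contrast. A model without the strata still counts that contribution as residual noise. Its standard errors are then larger than the true sampling variability: intervals are too wide, the test falls below its nominal level, and some power is lost.

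On these endpoints a conservative test is not automatically the safe direction, because itch and HDL are where the programme has seen unwanted effects. Protocol 1.4.2 reports pruritus in about 51% of subjects at 2.5 mg against under 5% on placebo. It also reports an LS mean HDL change of -8.3 mg/dL against -0.15. Needless imprecision makes such effects slightly harder to see. With the biopsy endpoints cancelled, the itch and lipid models are among the few inferential comparisons left.

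A second issue is missing data. An MMRM relies on data being missing at random given what the model contains. If diabetes status or background medication predicts both dropout and outcome, leaving it out makes that assumption harder to defend.

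**Working it through.** The plan states no figure for this point, and the sample-size section is redacted, so there is nothing to reproduce beyond 3 x 112 = 336.

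**Inputs from the documents.** 112 subjects per arm, 1:1:1 (protocol 5.6); two-sided alpha 0.05 for secondary tests (SAP 8.1 and 8.6.3).

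**Assumed input.** R2, the share of residual variance that the two factors explain after the baseline value and NAS. The documents give no value, so a range is shown.

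**Formulas.** With balanced strata, the true variance of a two-arm difference is s2(1 - R2)(2/n). The model without strata estimates it as s2(2/n). Hence:
- SE inflation = 1/sqrt(1 - R2)
- true size = 2[1 - Phi(1.960/sqrt(1 - R2))]
- power without strata, for an effect giving 80% power with them = 1 - Phi(1.960/sqrt(1 - R2) - 2.802), where 2.802 = 1.960 + 0.842

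Example, R2 = 0.10: 1/sqrt(0.90) = 1.054; 1.960 x 1.054 = 2.066; size = 0.039; power = 1 - Phi(2.066 - 2.802) = 0.769.

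| R2 (assumed) | SE too large by | True size of 5% test | Power (80% if adjusted) |
|---|---|---|---|
| 0 | 0% | 5.0% | 80.0% |
| 0.02 | 1.0% | 4.8% | 79.4% |
| 0.05 | 2.6% | 4.4% | 78.5% |
| 0.10 | 5.4% | 3.9% | 76.9% |

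n cancels from all three formulas, so these results do not depend on how many subjects were enrolled before termination, apart from small-sample effects.

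**Simulation check.** Linear model at one visit with complete data: 336 subjects, blocks of 6 within strata, 4000 replicates, and assumed prevalences of 50% (diabetes) and 15% (Vitamin E/pioglitazone).
- Rejection under no effect, without against with the factors: 4.2% against 5.0% at R2 = 0.05, and 4.0% against 5.4% at R2 = 0.10. The Monte Carlo standard error near 5% is sqrt(0.05 x 0.95/4000) = 0.34 percentage points.
- Power for a true difference of 0.36 SD: 76.7% against 78.0%, and 77.4% against 80.6%.
- Mean estimate for that difference: 0.360 in both models at both values of R2, so no bias.
- At R2 = 0.10 under no effect, the mean model SE without the factors was 0.134, against an actual spread of 0.128.

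The simulation agrees with the formulas in direction and approximate size. It did not include repeated visits or dropout.

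**The case against.** The case for leaving this alone has real force. The SAP follows the protocol's own MMRM terms, so it is not a deviation, and the protocol says only that an MMRM may be used. The endpoints are secondary and outside the multiplicity scheme. The error does not inflate false positives. Each model already adjusts for the parameter's baseline value, which may absorb much of any stable background effect; R2 could be near zero, and then nothing is lost. All of this stands, and it limits the severity. It does not explain why one model family departs from the others.

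Several stronger readings are tempting, and the documents do not support them:
- **Background treatment confounds these comparisons, or the trial's control of it is lost.** Control comes from stratified allocation and from the stable-regimen rules (protocol 3.1, 5.8.1 and 5.9.3), whatever the model contains.
- **NAS was put in place of the strata.** NAS is in the logistic and ANCOVA models too.
- **Lipids are hit hardest because diabetes and pioglitazone act on lipid metabolism.** The documents do not establish this for background diabetes or pioglitazone, and the point does not need it.
- **Dropout biases the contrast.** A route exists: starting a GLP-1 or PPAR agonist triggers early termination procedures (protocol 5.9.3), which may fall mainly on diabetic subjects. As a purely assumed illustration, let half the subjects be diabetic, let diabetes explain 10% of variance, and let retention be 70% (diabetic) and 90% (other) on active and 90% on placebo. The diabetic share on active becomes 0.35/(0.35 + 0.45) = 43.75% against 50%. The diabetes effect is sqrt(0.10/0.25) = 0.63 SD, so the contrast shifts by 0.0625 x 0.63 = 0.04 SD. The SE is sqrt(1/89.6 + 1/100.8) = 0.145 SD, so the shift is about 0.3 SE. No retention figure is given in the documents, earlier visits in an MMRM would reduce the shift, and dropout by Week 12 may be smaller. This is a reason to include the factors, not evidence of bias.

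**Conclusion.** The point holds as an unexplained inconsistency between models with a modest cost. The MMRMs for VAS, 5D-itch, TG, TC, HDL and LDL omit both stratification factors that the logistic and ANCOVA models include. For R2 from 0 to 0.10, standard errors are 0% to 5.4% too large, the 5% test runs at 5.0% down to 3.9%, and power falls by 0 to 3.1 points from 80%. R2 is an assumption throughout. The complete-data check showed no bias; the missing-at-random concern is a possibility that the documents do not let one size.

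The reach is limited. Section 9 implies, rather than states, that MMRM inference survives up to Week 12. A reader might count adiponectin and the subgroup MMRM among the affected analyses, but section 9 cancels both. Severity is minor to moderate. Confidence is high for the omission and lower for its size.

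**What to change.** Add diabetes status and Vitamin E/pioglitazone use, as recorded for randomisation, as fixed effects to the MMRM in SAP 8.6.1, 8.6.3.2.1 and 8.6.3.2.4, matching the ANCOVA. In Appendix A, add `diab_st` and `vitE_pio` to the CLASS and MODEL statements of the MMRM code. If the omission is deliberate, state the reason instead.

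Protocol 11.1 allows SAP changes only before unblinding. If unblinding has already occurred, report the adjusted model in the CSR as a justified deviation, as SAP section 1 provides. The same should be done for the protocol 11.6.1 wording, or the difference from it recorded in SAP section 9.

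The cost is two degrees of freedom and a few words of text and code. Both variables are already collected and used in the other models.

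While that code is open, two separate slips need attention: the REPEATED statement names treatment rather than visit, and the visit variable is spelled differently in the LSMEANS statement than in the CLASS and MODEL statements.
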